### **General Investigational Plan**

Evaluate the efficacy and safety of the natural plant medicine compound BBD-1 multi-target immune enhancement targeting agent in the treatment of hypersensitivity reaction (IgA) vasculitis.

Comparing the efficacy of natural plant medicine compound BBD-1 multi-target immune enhancement targeting agent with glucocorticoids, providing reference for clinical doctors to register BBD-1 multi-target immune enhancement targeting agent and use it reasonably and standardly in the future

05/07/2026

**Comparing the efficacy of natural plant medicine compound BBD-1 multi-target immune enhancement targeting agent with glucocorticoids, providing reference for clinical doctors to register BBD-1 multi-target immune enhancement targeting agent and use it reasonably and standardly in the future.**

1. IgA vasculitis is a common vascular allergic disease, and its etiology is not yet clear. It may involve factors such as infection, immune disorders, and genetics. It belongs to the category of immune diseases. This disease can be divided into simple type, abdominal type, joint type, renal type, and mixed type allergic purpura according to the location of onset. The annual incidence rate is about 6.1 to 55.9 cases per 100000 people. The highest incidence rate is among children aged 2 to 6 years. When the kidneys are affected, this condition is called IgAV nephritis (IgAVN), affecting approximately 20% to 80% of IgAV patients, making it one of the most common secondary glomerular diseases in this population. Meanwhile, the skin redness, itching, and joint pain caused by IgA vasculitis also seriously affect the quality of life of patients. Most IgAVN cases are mild or self limiting; However, some patients may experience severe kidney involvement, manifested as nephrotic syndrome, significant proteinuria, elevated serum creatinine levels, hypertension, persistent proteinuria, and kidney biopsy results showing more than 50% crescent shaped involvement. Research has shown that approximately 10% to 20% of patients with moderate to severe proteinuria caused by IgAVN may develop end-stage renal disease (ESRD), and persistent proteinuria has been identified as an independent risk factor for poor prognosis of IgAVN. At present, clinical treatment mainly relies on immunosuppressants such as nonsteroidal anti-inflammatory drugs, glucocorticoids, anti allergic and antihistamines, anticoagulants, corticosteroids, calcineurin inhibitors (CNI), mycophenolate mofetil (MMF), cyclophosphamide (CTX), etc. However, some patients may not respond well to conventional treatment, and long-term use of these drugs may lead to various adverse reactions, including infections, metabolic disorders, and growth disorders.

2. Previous studies have confirmed that BBD-1 multi-target immune enhancement targeting agent is effective and safe in treating hypersensitivity reaction (IgA) vasculitis. After 1 hour of intervention and treatment with BBD-1 multi-target immune enhancing targeted agent, itching disappeared and pain significantly reduced. After 24 hours, the purpura decreased, and after 48 hours, the purpura significantly decreased. After 72 hours, the purpura and pain basically disappeared, and reached the clinical cure standard after 96 hours.

3. Number of participants: 300 in Phase III clinical trials.

4. Inclusion criteria: Medically confirmed small vessel vasculitis with IgA deposition IgA vasculitis; Purpura and/or involvement of at least one organ in the kidneys, joints, or intestines.

5. Drug comparison: Glucocorticoids

Participant Group	Intervention/Treatment
Natural herbal compound BBD-1 multi-target immune enhancing targeting agent Lasting for 14 days	Natural herbal compound BBD-1 multi-target immune enhancing targeting agent 

8 capsules three times a day (morning, middle and evening) each time, 24 capsules per day (capsule) and 10 sprays on the affected area (spray) (the dosage of children above is halved)

Placebo control group placebo Placebo, lasting for 14 days	Drug glucocorticoid prednisone: 0.5-1 mg/kg per day for children and 30-40 mg/d for adults, taken in divided doses, gradually reduced after symptom relief (such as 10% reduction per week).

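### Kidney involvement of any severity qualifies for entry, but the BBD-1 group is listed only capsules and spray, no renal result is cited, and no rule covers severe nephritis

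*Protocol*

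**What the plan says.** All references are to the Protocol, General Investigational Plan.

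- **Entry (item 4).** Confirmed IgA vasculitis with purpura and/or "involvement of at least one organ in the kidneys, joints, or intestines". No threshold is given for proteinuria, creatinine, blood pressure or biopsy grade.
- **Severe renal forms (item 1).** The background says that "some patients may experience severe kidney involvement, manifested as nephrotic syndrome, significant proteinuria, elevated serum creatinine levels", and continues the list with "hypertension, persistent proteinuria, and kidney biopsy results showing more than 50% crescent shaped involvement".
- **Prognosis (item 1).** It states that "approximately 10% to 20% of patients with moderate to severe proteinuria caused by IgAVN may develop end-stage renal disease (ESRD"). It also says "Most IgAVN cases are mild or self limiting".
- **BBD-1 treatment (table).** The row gives "24 capsules per day (capsule) and 10 sprays on the affected area (spray"), for 14 days, with a reduced dose for children. No other treatment is listed.
- **Prior BBD-1 evidence (item 2).** It makes a general claim that the agent works and is safe in this disease, then gives a time course for itching, pain and purpura: "After 72 hours, the purpura and pain basically disappeared, and reached the clinical cure standard after 96 hours". The cure standard is not defined.
- **Control treatment (table).** The row is labelled "Placebo control group placebo Placebo, lasting for 14 days", but its treatment cell specifies prednisone with a gradual taper.

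**The concern.** The protocol describes a high-risk renal subgroup in its background and then writes an entry criterion that lets that subgroup in. For current care, item 1 names glucocorticoids, calcineurin inhibitors, mycophenolate and cyclophosphamide among others; none of these appears in the BBD-1 row. The specific results in item 2 are skin and pain outcomes over four days, so they give no basis for expecting an effect on the kidney.

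Two things are at stake. The first is patient safety: an investigator who enrols a patient with nephrotic syndrome or rising creatinine finds nothing in the document on whether to add treatment, or when. The second is interpretation: the stated aim is to guide registration and use of BBD-1, and a trial open to all renal severity could be read as covering severe nephritis when nothing in the plan is set up to support that.

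**Working it through.** No figure in the plan can be reproduced for this point. The 300 participants come without a derivation or an allocation ratio, and the question is one of eligibility and treatment. The check is therefore a reading of the sections against each other, followed by a test of whether the exposure can be sized.

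**Reading**

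1. Does item 4 admit severe renal disease? Yes. Kidney involvement is a named route of entry, and because of the and/or wording it can be the only one. No severity limit follows. Items 1 to 5 are numbered consecutively and none is for exclusions, but the point rests on item 4's own wording.
2. Does the document recognise severe renal disease as distinct? Yes, in item 1, with a list of signs.
3. Is a renal treatment listed for the BBD-1 group? No. The row holds capsules and spray only. Nothing says that other treatment is withheld, and nothing says that it is permitted.
4. Is a renal result cited for BBD-1? No. Item 2 gives itching, pain, purpura and an undefined cure standard, plus the general efficacy and safety claim.
5. Does the control label change the answer? The aim, item 5 and the treatment cell all point to a glucocorticoid. On that reading the gap concerns the BBD-1 group. If the control group really received placebo, it would concern both groups. The mislabelling is a separate matter.

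**Can the exposure be sized?**

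Inputs: 300 participants (item 3); nephritis in 20% to 80% of patients (item 1). Assumed, because not stated: 1:1 allocation, and enrolment that mirrors item 1.

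- BBD-1 group: 300 / 2 = 150.
- With nephritis of any grade: 150 × 0.20 = 30 to 150 × 0.80 = 120.
- If one third to two thirds of participants were allocated to BBD-1 instead: 100 × 0.20 = 20 to 200 × 0.80 = 160.

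The severe share of nephritis is not given. For illustration only, take an assumed share of 1% to 10%, with 150 in the group:

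| Nephritis share | Severe share (assumed) | Expected severe | Chance of at least one |
|---|---|---|---|
| 20% | 1% | 150 × 0.20 × 0.01 = 0.3 | 1 − 0.998^150 = 0.26 |
| 20% | 10% | 150 × 0.20 × 0.10 = 3 | 1 − 0.98^150 = 0.95 |
| 80% | 1% | 150 × 0.80 × 0.01 = 1.2 | 1 − 0.992^150 = 0.70 |
| 80% | 10% | 150 × 0.80 × 0.10 = 12 | 1 − 0.92^150 > 0.999 |

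A range of 0.3 to 12 patients, driven by an assumed share, is no estimate and sets no floor. It shows only that the number depends on something the document does not state.

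**Can the harm be sized?** No. The 10% to 20% figure comes without a time horizon or treatment status, and the document says nothing about the effect of a 14-day period on renal outcome.

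**The case against.** The strongest opposing case has four parts.

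- **The treatment row describes the study drug, not all care.** This is correct. A reader might infer that BBD-1 patients are denied steroids or rescue treatment. The document does not say so; it is silent. What remains is that silence gives the investigator no rule for a patient whose kidneys are severely affected.
- **The renal stake is exaggerated.** A reader might infer that 10% to 20% of exposed patients would reach end-stage disease because of the trial. That figure describes patients with moderate to severe proteinuria in general, it is not an added risk, and treatment with BBD-1 lasts 14 days. It supports calling the group high risk and nothing more.
- **Renal evidence may exist.** Item 2 refers to previous studies and claims efficacy and safety in general terms. Whether those studies measured renal outcomes cannot be told from the document. The fair statement is that no renal result is cited.
- **Breadth was intended, and most nephritis is mild.** This is also fair. It argues against making every sign in item 1 an exclusion on its own: without cut-offs, any notable or lasting proteinuria, or hypertension alone, could remove much of the renal type that item 4 means to include. An entry exclusion also does nothing for a patient who enters with mild disease and worsens. Both points shape the remedy; neither removes the gap.

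**Conclusion.** The point holds in a limited form. Item 4 sets no renal severity limit, item 1 names severe renal forms, the BBD-1 row lists only capsules and spray for 14 days, and the cited results contain nothing renal. Following the plan as written can therefore put a patient with severe nephritis on BBD-1 with no stated rule for other treatment. This should be corrected, because eligibility and escalation belong in the protocol and would not be expected in a statistical analysis plan.

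Its size is unknown. Under 1:1 allocation and enrolment that mirrors item 1, 30 to 120 BBD-1 patients would have nephritis of some grade; how many would be severe cannot be derived. The document supports neither a count of severe cases nor an estimate of excess harm.

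**What to change.** 1. **Entry.** Add to item 4 an exclusion of severe renal involvement: nephrotic syndrome, elevated serum creatinine, more than 50% crescents where a biopsy has already been done, or proteinuria above a cut-off. The sponsor must set the proteinuria cut-off and the creatinine limit, since the document gives neither. Require routine urine protein, serum creatinine and blood pressure at entry. Keep mild nephritis eligible, and do not use hypertension alone as an exclusion.
2. **After entry.** State that a patient in either group who develops these signs goes to standard treatment and remains in the analysis.
3. **Conclusions.** State that the trial supports no conclusion about severe nephritis.

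The cost is one exclusion, one escalation sentence and routine checks at entry; no new biopsy is required. Fewer renal patients will be eligible, by an amount that depends on the proteinuria cut-off and cannot be stated now. The results will not apply to severe nephritis.
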